8.2.1 Vital Signs, Body Weight, and Height

Planned time points for vital signs, body weight, and height are provided in the SoA (Section 1.3). Additional vital signs may be taken at any other times, if deemed necessary.

Heart rate and blood pressure measurements will be performed with subjects in a supine position for at least 5 minutes, except when they are seated or semi-reclined because of study procedures and/or AEs (e.g., nausea, dizziness), or if deemed necessary by the Investigator or designee. Blood pressure measurements should be measured on the same arm throughout the study.

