8.2.2 Clinical Laboratory Testing

A list of clinical laboratory tests to be performed is provided in Appendix 2.

The clinical safety laboratory tests will be performed at a central laboratory. Samples for complete blood count (CBC) and chemistry should be obtained and analyzed based on central lab requirements. Laboratory safety tests may be performed at various unscheduled time points, if deemed necessary by the Investigator or designee.

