8.1.2 Assessment Time Windows

The following study visits are scheduled:

Table 8-1: Assessment Time Windows

Visit	Analysis Visit Number	Window	Target Day
Screening	0	Day -30 to Day 1	N/A
Visit 1/Day 1	1	Day 1	1
Visit 2 /Week 6	2	After Day 1 to Week 8	43
Safety Follow-up 1	3	1-3 days after second infusion	1 day after second infusion date
Safety Follow-up 2/EOS/ET	4	28 (25-31) days after second infusion	28 days after second infusion date

All scheduled visits including assessments performed outside the target window, will be included in summary tables, figures, and listings. Scheduled visit data will be presented according to the nominal CRF recorded visit. Early termination visit and unscheduled visit data will be mapped to scheduled visits using the windows in Table 8-1. Early termination visit and unscheduled visit data will be included in tables and figures if no scheduled visit data is available for the nominal CRF recorded visit. If more than one unscheduled assessment (early termination or unscheduled) is performed within an analysis window for a visit without a nominal CRF record, the assessment performed closest to the target day will be used, if there is a tie, the earlier assessment will be used.

For clinical laboratory evaluation tables, early termination visits and unscheduled safety data will be mapped to scheduled visits using analysis windows. For all other safety tables and figures, early termination visits and unscheduled safety data will not be mapped to scheduled visits using analysis windows. All data, scheduled and unscheduled, will be included in listings.

Page 16 of 38

Version Date: 2022-12-16 Version: 2.0

Document Control No.: TMP-SA-008-01 Template Effective Date: 23 Mar 2021

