9.6 Vital Signs

Baseline and all post-baseline visit values and change from baseline to post-baseline values in systolic blood pressure, diastolic blood pressure, heart rate, weight, and body mass index (BMI) will be summarized for the Safety Set using descriptive statistics, as described in Section 4. Height at baseline will be summarized using descriptive statistics, as described in Section 4, and will be used in the calculation of BMI at post-baseline visits.

Vital sign results by visit will be presented in a data listing for subjects in the Safety Set.

Vital signs with clinically significant changes will be summarized and listed as 'flagged' based on the Sponsor's internal guidelines based on Appendix 14.3.

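### SAP 8.1.2 states no route for unscheduled vital signs, and only a conditional one for unscheduled laboratory values, into the clinically significant change tables (14.3.3.4 and 14.3.4.2), so these may undercount

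*SAP*

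**What the plan says.** SAP 8.1.2 contains four rules that bear on this point.

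- **General rule.** Early-termination and unscheduled data are assigned to visits by the Table 8-1 windows, but "unscheduled visit data will be included in tables and figures if no scheduled visit data is available for the nominal CRF recorded visit". If several such values fall in one window, the one nearest the target day is taken, and the earlier one on a tie.
- **Laboratory tables.** "For clinical laboratory evaluation tables, early termination visits and unscheduled safety data will be mapped to scheduled visits using analysis windows". SAP 9.5 refers back to this rule.
- **Other safety outputs, which include vital signs.** "For all other safety tables and figures, early termination visits and unscheduled safety data will not be mapped to scheduled visits using analysis windows".
- **Listings.** "All data, scheduled and unscheduled, will be included in listings".

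SAP 9.6 then says: "Vital signs with clinically significant changes will be summarized and listed as" flagged, using the criteria in Appendix 14.3. SAP 9.5 says the same for laboratory parameters. The outputs are Tables 14.3.3.4 and 14.3.4.2. Neither section says which values feed them: no worst-value rule, no any-value rule and no exception to 8.1.2.

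The protocol expects unscheduled measurements. On vital signs, Protocol 8.2.1 says: "Additional vital signs may be taken at any other times, if deemed necessary". On laboratory tests, Protocol 8.2.2 says: "Laboratory safety tests may be performed at various unscheduled time points, if deemed necessary by the Investigator or designee".

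**The concern.** Restricting by-visit means and changes to scheduled data is sensible, because it stops subjects with extra measurements from distorting the averages. A threshold summary has a different purpose: to find extreme values. Readings taken because something is suspected are the ones most likely to cross a threshold, and the 8.1.2 rules, written for by-visit tables, tend to filter them out.

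Safety is the study's only secondary objective, and laboratory and vital-sign changes are named endpoints. Protocol 7.1.1.1 lists hypotension among the symptoms suggesting an infusion-related reaction and counts any event on the first day of the infusion as potentially one. Yet only one post-dose blood pressure is scheduled per dose, and no laboratory sample is scheduled between dose 1 and the week before dose 2. Unscheduled readings are therefore the main source of numeric data on an acute change outside those points.

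**Working it through.** The plan gives no figure to reproduce. The check traces what happens to each kind of unscheduled value under the rules as written.

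**Inputs**

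- Scheduled laboratory samples: Screening, within 7 days before dose 2, and Safety Follow-up 1 (Protocol 1.3, note h).
- Scheduled vital signs: within an hour before dosing and 5-10 minutes after it (Protocol 1.3, note d).
- Windows (SAP Table 8-1): Visit 1 is Day 1; Visit 2 runs from after Day 1 to Week 8 with target Day 43; Safety Follow-up 1 is 1-3 days after the second dose.
- Post-baseline laboratory visits: Visit 2 and Safety Follow-up 1 only (SAP 9.5).

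**Trace**

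| Unscheduled value | Window | If the scheduled value exists | If it is missing |
|---|---|---|---|
| Laboratory, Day 1 after dose 1 | Visit 1 (Screening also runs to Day 1) | Left out: not a post-baseline visit in SAP 9.5 | Left out for the same reason |
| Laboratory, after Day 1 and before dose 2 | Visit 2 | Displaced by the sample drawn before dose 2 | Enters; nearest to Day 43 is used |
| Laboratory, day of dose 2 after dosing | Visit 2 | Displaced by the sample drawn before dose 2 | Enters |
| Laboratory, 1-3 days after dose 2 | Safety Follow-up 1 | Displaced by the scheduled sample | Enters |
| Blood pressure or heart rate, any time | None: not mapped | No stated route in | No stated route in |

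**Timing of the displacing sample.** With dose 2 at Day 43, the Visit 2 sample can be drawn no earlier than Day 43 − 7 = Day 36, which is 36 − 1 = 35 days after dose 1. A test prompted by a suspected reaction soon after dose 1 is thus replaced by one taken about five or more weeks later. For subjects with a scheduled Visit 2 sample, Table 14.3.3.4 contains no acute value after dose 1.

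**Choice among several values.** Among values up to Day 43, nearest to target means latest. Where the scheduled Visit 2 sample is missing, an early abnormal value followed by a later recovered one is represented by the recovered one.

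**Internal conflict.** The first paragraph of rules in SAP 8.1.2 maps unscheduled and early-termination data generally; the second switches mapping off for every safety output except the laboratory tables. The two need to be reconciled whatever is decided about the flag tables.

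**The case against.** A reader might infer that readings prompted by a suspected reaction can never appear in the flag tables, and that safety will be reported as cleaner than the data. The documents do not support either statement in that form.

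- **Laboratory values are not shut out altogether.** They enter when the scheduled value is missing. A subject discontinued after a first-dose reaction has no scheduled Visit 2 value, so an unscheduled test after Day 1 can enter. This stands.
- **Not mapped is not the same as excluded.** The vital-sign sentence governs assignment to visits. If Table 14.3.4.2 is not organised by visit, unscheduled readings might still be used. Its title does not say by visit, and the table specifications are in separate documents (SAP 2). The title is weak evidence, since Tables 14.3.3.1 and 14.3.4.1 also lack the phrase although SAP 9.5 and 9.6 describe summaries by visit. Exclusion is the natural reading, but still an inference.
- **CRF design is not shown.** Protocol 8.2.4 links Unscheduled Visit CRFs to additional visits. An extra blood pressure during a dosing visit might be recorded under that visit. This stands as an unknown.
- **The values are not lost.** All are listed, and flagged values are to be listed as well as summarised. A reaction after administration is recorded as an adverse event (Protocol 7.1.1.1), and events starting on a dosing day are tabulated (SAP 9.4.1). This answers much of the concern, but not all. An abnormal value becomes an adverse event only if the investigator judges it clinically significant, and findings associated with the underlying disease generally do not qualify (Protocol 10.3.1). The flag tables apply fixed numeric criteria without that judgement.

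**Conclusion.** The point holds as a possible undercount in two threshold-based summaries. For a subject with complete scheduled data, the written rules leave an unscheduled laboratory value out of Table 14.3.3.4. On the natural reading they leave an unscheduled blood pressure out of Table 14.3.4.2. The first conclusion rests on the text of SAP 8.1.2 and 9.5. The second also assumes that the vital-sign flag table follows the mapping rule and that extra readings are recorded as unscheduled.

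The size cannot be estimated, because the documents do not say how often unscheduled readings are expected. Two figures are tempting and should not be taken as the size:

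- The scheduled post-dose blood-pressure window is 5 minutes wide, and the scan follows 270 to 330 minutes after the start of administration: 5/330 = 1.5% to 5/270 = 1.9%. That is a share of clock time set by the protocol's schedule. It is not a probability of missing an event, and changing the SAP would not alter it.
- One omitted subject is 1/20 = 5 percentage points only if the Safety Set is exactly 20. Subjects without a second dose or scan are replaced (Protocol 5.5), so the denominator can be larger.

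This should be corrected because SAP 2 gives the SAP primacy over the protocol, and its text does not establish the more useful analysis even if the sponsor intends it.

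**What to change.** In SAP 8.1.2, 9.5 and 9.6, state that Tables 14.3.3.4 and 14.3.4.2 use all post-baseline values, scheduled and unscheduled. Count a subject once per parameter if any value meets the Appendix 14.3 criterion, separately for the period after dose 1 (up to dose 2) and the period after dose 2. Leave the by-visit descriptive tables unchanged. At the same time, reconcile the two paragraphs of 8.1.2 on mapping. If the sponsor prefers scheduled values only in the flag tables, the SAP should say so and the tables should carry a footnote.

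The cost is a few sentences and a small programming change. The downside is that flag counts may rise slightly, because symptomatic subjects are measured more often; a footnote can say so. If the SAP can no longer be amended before database lock, the any-value version can be added and identified in the study report as unplanned, as Protocol 9.5 allows.

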8.1.3 Timing of Analyses

All final analyses will be performed after the study is completed and the database is locked.

8.1.4 Multiple Comparisons/Multiplicity

No adjustments for multiple comparisons will be made. Any p-values will be considered descriptive.

8.2 Primary Endpoint

The repeatability of organ-specific quantitation of radiotracer uptake will be assessed using PET/CT imaging of ¹²⁴I-AT-01 in subjects with AL or ATTR systemic amyloidosis and will be presented using multiple methods by organ (heart, liver, spleen, and kidney) to explain the relationship and describe the variability between assessments. The quantitative methods that will be used are (1) repeatability coefficients, (2) Bland-Altman plots, (3) Intraclass Correlation Coefficients (ICC), and (4) Signal-to-Noise Ratio and Contrast-to-Noise Ratio vs SUV-based metrics plots. There are 3 readers at each time point and 2 reads per scan per reader for quantitative reads. The above quantitative methods will be deployed to measure multiple types of repeatability.

These methods are described in more detail in sections 8.2.1, 8.2.2, 8.2.3, and 8.2.4.

The SUV-based metrics are peak SUV (denoted SUVpeak, collected as suv_peak_organ from the imaging dataset), and max SUV (denoted SUVmax, collected as suv_max_organ from the imaging dataset).

In addition to the above quantitative methods, AT-01 uptake will be visually determined by three expert radiologists for each scan of each organ. Agreement among the three reads will be evaluated by scan using Fleiss' kappa. Agreement between each reader's two scans will be evaluated using Cohen's kappa. Details are described in section 8.2.5.

The quality of imaging results will be taken into consideration such that any images with a "Not Readable" indication of scan image quality will be excluded from primary analyses.

All imaging results will be listed.

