7.0 DISCONTINUATION OF STUDY INTERVENTION AND/OR SUBJECT DISCONTINUATION OR WITHDRAWAL

7.1 Discontinuation of Study Intervention

All subjects are free to withdraw from participating in this study at any time for any reason, specified or unspecified, and without prejudice. No constraints will be placed on ordinary subject management.

Subjects will be withdrawn for any of the following reasons:

- The subject withdraws consent.
- The subject does not have amyloid deposits in the heart, liver, spleen or kidney on the Day 1 PET/CT scan, as described in Section 8.1.4.
- The subject begins treatment with heparin or a heparin analog within 7 days of a planned administration of ¹²⁴I-AT-01, as described in Section 7.1.1.2.
- The subject experiences an intolerable AE or serious AE (SAE).
- The subject enrolls into another clinical study in which an investigational treatment or approved therapy for investigational use is administered.
- The subject becomes pregnant. Study treatment must be discontinued immediately. Report the pregnancy according to the instructions in Section 8.3.5.
- The subject is unwilling or unable to comply with the protocol.
- At the discretion of the Investigator or Sponsor.
- Investigator decision that it is not in the best medical interest of the subject to continue participation in the investigation.
- The Sponsor prematurely terminates the study.

Prior to discontinuing a subject, every effort should be made to obtain as much follow-up data as possible. Withdrawn or discontinued subjects will undergo ET activities per the SoA (Section 1.3). Subject withdrawals will be documented clearly on the source documents and applicable case report forms (CRFs). Subject withdrawals will be documented clearly on the source documents and applicable CRFs.

Discontinued subjects will be assessed for adverse events via a telephone call 24-48 hours after decision to discontinue.

Notification of subject withdrawals will be made to the Sponsor, or designee.

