8.2.5 Inter-rater and Intra-rater Agreement

AT-01 uptake is determined by three expert radiologists determination of AT-01 uptake for each region, it is one evaluation per expert per organ per visit. The number and % of subjects with positive AT-01 uptake will be described by expert by visit and organ. The inter-rater agreement in positive AT-01 uptake between the three expert radiologist's determination by visit will be presented using Fleiss' kappa. The intra-rater agreement in positive AT-01 uptake between Scan 1 and Scan 2 in each expert radiologist's determination by expert will be presented using Cohen's kappa and its 95% confidence interval.

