15 ATTACHMENTS

15.1 Table of Contents for Data Display Specifications

Tables		
Number	Title	Population
14.1.1	Summary of Subject Disposition	All Subjects
14.1.2.1	Summary of Subject Demographics and Baseline Characteristics	Safety
14.1.3.1	Medical History by System Organ Class and Preferred Term	Safety
14.1.3.2	Surgical or Procedural History by System Organ Class and Preferred Term	Safety
14.1.4.1	Summary of Prior Medications by Drug Class and Preferred Term	Safety
14.1.4.2	Summary of Concomitant Medications by Drug Class and Preferred Term	Safety
14.1.4.3	Summary of Prior Medications for the Treatment of Systemic Amyloidosis by Drug Class and Preferred Term	Safety
14.1.4.4	Summary of Concomitant Medications for the Treatment of Systemic Amyloidosis by Drug Class and Preferred Term	Safety
14.1.5	Summary of Protocol Deviations	Enrolled
14.1.6	Summary of Treatment Exposure	Safety
14.2.1.1.1	Within Reader Repeatability Coefficients by Reader, Visit, and SUV Metric by Organ	Image Evaluable Set
14.2.1.1.2	Within Reader Repeatability Coefficients by Reader, Visit, and SUV Metric by Organ and Amyloid Type	Image Evaluable Set

Page 33 of 38

14.2.1.2.1	Between Visit Repeatability Coefficients by Reader and SUV Metric by Organ	Image Evaluable Set
14.2.1.2.2	Between Visit Repeatability Coefficients by Reader and SUV Metric by Organ and Amyloid Type	Image Evaluable Set
14.2.1.3	Summary of Repeatability Analysis Results	Image Evaluable Set
14.2.2.1	Among Reader Intraclass Correlation Coefficients by Visit and SUV Metric by Organ	Image Evaluable Set
14.2.2.2	Among Reader Intraclass Correlation Coefficients by Visit and SUV Metric by Organ and Amyloid Type	Image Evaluable Set
14.2.3.1	Summary of Inter-rater Agreement by Visit by Organ	Image Evaluable Set
14.2.3.2	Summary of Intra-rater Agreement by Expert Radiologist by Organ	Image Evaluable Set
14.2.4	Coefficients of Variation by Visit by Organ	Image Evaluable Set
14.3.1.1	Overall Summary of Treatment-Emergent Adverse Events	Safety
14.3.1.2	Treatment-Emergent Adverse Events by System Organ Class and Preferred Term	Safety
14.3.1.3	Treatment-Emergent Adverse Events by System Organ Class, Preferred Term, and CTCAE Grade	Safety
14.3.1.4.1	Treatment-Emergent Adverse Events by System Organ Class, Preferred Term, and Relationship to AT-01	Safety
14.3.1.4.2	Treatment-Emergent Adverse Events by System Organ Class, Preferred Term, and Relationship to KI	Safety

Page **34** of **38**

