16.2.4.6	Pregnancy Test Results	Safety
16.2.5.1	¹²⁴ I-AT-01 Administration	Safety
16.2.5.2	Potassium Iodide Administration	Safety
16.2.6	Imaging Results	Image Evaluable
16.2.7.1	Adverse Events by Subject, System Organ Class, and Preferred Term	Safety
16.2.7.2	Treatment-Emergent Adverse Events on Day of Dosing by Subject, System Organ Class, and Preferred Term	Safety
16.2.7.3	Treatment-Emergent Adverse Events on Day of Dosing Reported on the AT01 Administration CRF	Safety
16.2.8.1	Laboratory: Chemistry	Safety
16.2.8.2	Laboratory: Hematology	Safety

Page **37** of **38**

Version Date: 2022-12-16 Version: 2.0

Document Control No.: TMP-SA-008-01 Template Effective Date: 23 Mar 2021

Attralus, Inc.

 $Statistical\ Analysis\ Plan-AT01-001$

16.2.8.3	Laboratory: Urine and Biomarker Results	Safety
16.2.8.4	Vital Signs	Safety

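### The SAP promises to list all imaging results but limits the listing, and the inter-rater table, to subjects with an evaluable pair of scans, so Day 1 reads of subjects stopped for a negative scan are not shown

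*SAP*

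**What the plan says.** SAP 8.2 excludes images rated not readable from the primary analyses and then states, without restriction, "All imaging results will be listed". In SAP 15.1 the only imaging listing is 16.2.6; its title and population columns read "Imaging Results Image Evaluable".

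SAP 8.2.5 plans three visual-read summaries:

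- Percent positive: "The number and % of subjects with positive AT-01 uptake will be described by expert by visit and organ". No population is named here, and no title in SAP 15.1 mentions this summary.
- Fleiss' kappa among the three experts at each visit. Table 14.2.3.1 appears as "Summary of Inter-rater Agreement by Visit by Organ Image Evaluable Set".
- Cohen's kappa between Scan 1 and Scan 2 for each expert. Table 14.2.3.2 appears as "Summary of Intra-rater Agreement by Expert Radiologist by Organ Image Evaluable Set".

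SAP 5 defines the IES as subjects scanned both on Day 1 and 6 to 8 weeks later, with evaluable images both times, and assigns it to the repeatability analyses. Protocol 9.4 agrees.

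Protocol 7.1 gives as a reason for withdrawal: "The subject does not have amyloid deposits in the heart, liver, spleen or kidney on the Day 1 PET/CT scan". Protocol 4.1.3.1 and 8.1.4 add that such subjects receive no second administration and have no second scan.

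**The concern.** The text of SAP 8.2 and the population given for Listing 16.2.6 cannot both be followed. A Day 1 scan exists for every subject stopped because it was negative, yet none of these subjects can enter the IES. The listing would also lose Day 1 scans of subjects who drop out for other reasons, such as an infusion reaction, heparin use or withdrawal, and both scans of a subject with one unreadable image.

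The loss through negative scans matters most because it depends on the outcome: the Day 1 result decides whether the Day 1 result is shown. Percent positive at one visit and agreement among readers at one visit do not need a second scan. Computed on the IES, the Day 1 rows would describe a group selected for being positive. Protocol 5.5 has subjects without a second dose or scan replaced, so the imaging tables could look complete while these reads are absent.

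**Working it through.** The documents give no expected percent positive and no expected number of all-negative subjects, so there is no stated figure to reproduce.

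**Inputs**

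- IES definition: SAP 5.
- Discontinuation rule: Protocol 4.1.3.1, 7.1 and 8.1.4.
- Planned size, up to 20: SAP 3.3 and Protocol 9.3.
- Detection in one or more organs in more than 90% of patients in the earlier study: Protocol 2.2.2.
- Share of subjects negative in all four organs, q: not given. Assumed at 2%, 5% and 10%.

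**Step 1: set membership.** Negative in all four organs on Day 1 means no second scan, and hence not in the IES. A subject negative in some organs but positive in at least one remains eligible for it.

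**Step 2: percent positive.** Let N subjects be scanned on Day 1, k be removed as all-negative, and x be positive in a given organ. Ignore other losses, and assume that the discontinuation read agrees with the expert reads. The k subjects add nothing to the numerator, so:

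- all scanned: x/N
- IES: x/(N − k)
- ratio: N/(N − k) = 1/(1 − q), with q = k/N

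For N = 20 and k = 2:

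| Positive in organ (x) | All scanned | IES |
|---|---|---|
| 6 | 6/20 = 30.0% | 6/18 = 33.3% |
| 10 | 10/20 = 50.0% | 10/18 = 55.6% |
| 14 | 14/20 = 70.0% | 14/18 = 77.8% |

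With replacement, more than 20 may be scanned. For N = 22, k = 2 and x = 14, the figures are 14/22 = 63.6% and 14/20 = 70.0%.

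**Step 3: how likely and how large.** The chance of at least one all-negative subject in 20 is 1 − (1 − q)^20.

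| Assumed q | Ratio 1/(1 − q) | Chance of at least one in 20 |
|---|---|---|
| 2% | 1.02 | 33% |
| 5% | 1.05 | 64% |
| 10% | 1.11 | 88% |

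**Step 4: Day 1 kappa.** Take an illustrative two-reader table with 14 both positive, 1 and 1 discordant, and 2 both negative (n = 18).

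- Observed agreement 16/18 = 0.889; chance agreement (15×15 + 3×3)/18² = 0.722; kappa = (0.889 − 0.722)/(1 − 0.722) = 0.60.
- Add two both-negative subjects (n = 20): observed 18/20 = 0.900; chance (15×15 + 5×5)/20² = 0.625; kappa = (0.900 − 0.625)/(1 − 0.625) = 0.73.

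Fleiss' kappa behaves the same way. Write 1 − kappa = D/[2p(1 − p)], with D the mean pairwise disagreement and p the overall positive share. Adding unanimous negatives multiplies both D and p by the same factor s < 1, so 1 − kappa becomes D/[2p(1 − sp)], which is smaller. If the removed subjects are unanimous negatives and the remaining reads contain any disagreement, the IES value is therefore too low.

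**Step 5: what does not change.** Cohen's kappa between scans and every between-visit statistic need both scans, so the IES is the right set for them.

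**The case against.** The objective is repeatability, not detection. There is no hypothesis (Protocol 9.1), eligibility already selects subjects with known organ involvement, and percent positive is descriptive. Protocol 9.5.2 places reader agreement under the primary endpoint, and Protocol 9.4 assigns repeatability to the image-evaluable population, so using the IES for agreement tables is defensible. SAP 2 says that detailed display specifications are in separate documents, which may settle the population for percent positive. All of this stands and limits the weight of the point. It does not remove the conflict over the listing or supply the missing population in SAP 8.2.5.

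A reader might also infer more than the documents support:

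- *That Day 1 positivity is 100% by construction.* That would concern positivity in at least one organ, which is not a planned statistic; SAP 8.2.5 reports by organ. It would also require the discontinuation read to match the expert reads, and the documents do not say who makes that call.
- *That about 10% of subjects will be all-negative.* The earlier study's figure is more than 90% detected, so 10% is its edge, not its expected value. Its organs are not shown to be only these four (Protocol 2.3.1 adds pancreas), so the range stays an assumption.
- *That negative results vanish from the report.* Organ-negative reads of IES subjects remain, and SAP 6.1 tabulates and lists disposition, with reasons for discontinuation tabulated, for everyone who signed consent. What is missing is the reads of those outside the IES.
- *That the choice flatters every result.* For kappa it tends to work the other way.
- *That both visual-read tables have the wrong population.* Table 14.2.3.2 compares two scans and needs both.

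**Conclusion.** The conflict is certain from the text: SAP 8.2 promises all imaging results, and Listing 16.2.6 leaves out every scan of any subject without an evaluable pair. Table 14.2.3.1 also restricts Day 1 inter-rater agreement to the IES, although a second scan is not needed for it.

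The effect on percent positive is conditional. It arises if that summary uses the IES, which is plausible from Table 14.2.3.1 but unstated, and if at least one all-negative subject is stopped. Where the discontinuation read agrees with the expert reads, the relative inflation is modest, about 1.02 to 1.11 over the assumed 2% to 10%; with nobody all-negative it is zero. Day 1 Fleiss' kappa may be understated. For subjects lost for other reasons, the direction of any bias is unknown. The between-visit repeatability results are not affected. This merits correction because it removes an outcome-dependent selection at little cost; it does not undermine the primary analysis.

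**What to change.** - Set the population of Listing 16.2.6 to all subjects with any PET/CT scan, with an IES flag and a readability flag.
- State in SAP 8.2.5, and for Table 14.2.3.1, that Day 1 percent positive and Day 1 Fleiss' kappa use all subjects with a readable Day 1 scan. The whole Safety Set should not be used: it includes anyone given any amount of the agent, and a subject stopped for a reaction during administration may have no scan.
- Say which display carries the percent-positive summary.
- Keep the IES for Cohen's kappa between scans (Table 14.2.3.2) and for all between-visit analyses.

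No new data are needed beyond the expert reads of Day 1 scans; if scans outside the IES have not gone to the experts, they would have to be read. The cost is that the Day 1 and Visit 2 denominators will differ and need a footnote, and that Day 1 positivity may be slightly lower.
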